9.4 Treatment of Participants

9.4.1 Investigational Medicinal Product

Full information regarding the preparation, storage, and administration of NNZ-2591 Oral Solution, 50 mg/mL is provided in the Pharmacy Manual. NNZ-2591 IMP is provided as a ready-to-use strawberry-flavored liquid for oral administration.

9.4.2 Investigational Medicinal Product Administration

NNZ-2591 Oral Solution, 50 mg/mL will be administered open-label at a target dose of 12 mg/kg BID. The total administration period for NNZ-2591 will be 13 weeks. Participants will be up-titrated to the target dose according to the dosing schedule outlined in Section 7.2. The dose titration schedule may be modified based on updated PK modelling including data from the study.

NNZ-2591 Oral Solution, 50 mg/mL, is provided as a ready-to-use strawberry-flavored liquid for oral administration. The IMP should not be mixed with water, liquid thickeners, or food for administration.

Each day there will be two dose administrations, one in morning and one in afternoon or evening. There should be at least 8 hours between doses. Doses should be given on an empty stomach (2 hours after the previous meal or snack and 30 minutes prior to the next). Doses may be taken over a 10-minute period with a follow up of 250 mL of water.

For all participants, the total duration of NNZ-2591 treatment will be 91 days. Dosing at the end of Baseline counts as Day 1 whether one or two doses are given. Dosing may not exceed 91 days including Day 1, and all efficacy assessments for the EOT visit must be completed on or before Day 91 of treatment.

The first dose of IMP will be administered in the clinic after all Baseline assessments are completed or, if the Investigator judges that it is too late in the day, on the following day. The participant should be monitored for at least three hours after the first dose. If the first dose is administered the day following Baseline, vital signs (except height) should be collected before the dose is administered. Day 1 of dosing is defined by the date when the first dose is taken. At this visit, the site will provide IMP for the caregiver to dispense at home. Enough IMP will be provided to cover the interval until the next in-clinic visit when the caregiver will be re-supplied from site.

Within the up-titration period, if a participant is deemed not to be tolerating the current dose within the 2-week period, and they have not met any of the stopping criteria below (see Section 9.4.5), they can be down-titrated to the next lower dose in the titration schedule (See Section 7.2). The Investigator must attempt to increase the dose as soon as it is possible based on the clinical situation. The aim is to return to the originally assigned dose. If the originally assigned dose cannot be reached, or the participant is again unable to tolerate that dose, the Investigator will continue treatment on the highest dose the participant can tolerate. Stopping rules for the discontinuation of the administration of IMP are described in Section 9.4.5. Investigators are to discontinue administration of IMP if the participant meets any of the criteria described in Section 9.4.5.

Note that early cessation of IMP does not necessarily mean the participant is withdrawn from the study. With any early cessation, all evaluations and tests scheduled during the study must be conducted if possible.

9.4.3 Treatment Compliance

The timing of administration of the IMP should be at approximately the same time each day. Each day there will be two dose administrations, one in morning and one in afternoon or evening. There should be at least 8 hours between doses. Doses should be taken by mouth either from a cup or via a dosing syringe provided by the pharmacist. Doses should be given on an empty stomach (2 hours after the previous meal or snack and 30 minutes prior to the next). The IMP should not be mixed with water, liquid thickeners, or food for administration. Doses may be taken over a 10-minute period with a follow up of 250 mL of water.

The treatment times will be recorded in the Caregiver Diary and then entered into the eCRF. A Study Monitor will review participant source documents and drug accountability records to assess treatment compliance on an ongoing basis during site visits. Participants who receive \geq 80% and \leq 120% of IMP, administered in accordance with the protocol are considered compliant.

9.4.4 Protocol Deviations

This study will be conducted as described in this protocol, except during an emergency situation in which the protection, safety and well-being of the participant requires immediate intervention, based on the judgment of the Investigator (or appropriately qualified designee). In the event of a significant deviation from the protocol, the Investigator or designee must contact the Medical Monitor or Sponsor or their agent at the earliest possible time by telephone. This will allow an early joint decision regarding the participant's continuation in the study. The Investigator will document the outcome of the discussion in the source documents and e-CRF, and the Sponsor likewise will retain a documentary record of the decision. The Sponsor will reserve the right to recommend suspension or discontinued involvement of sites with excessive protocol violations.

9.4.5 Early Discontinuation

Investigational Medicinal Product administration may be stopped early if an AE, tolerability issue or inter-current illness occurs that in the opinion of the Investigator (or designee) necessitates cessation of the IMP. Study drug administration must be ceased for all SAEs considered related to the experimental medication.

Note that early cessation of IMP does not necessarily mean the participant is withdrawn from the study. With any early cessation, all evaluations and tests scheduled during the study must be conducted if possible.

- Requests early discontinuation.
- requires treatment with an excluded medication, as defined in Exclusion Criteria (Section 8.2).
- at any point in the study, a participant becomes ill with symptoms of/or tests positive for COVID-19 infection.
- has a positive pregnancy test or becomes pregnant.
- in the Investigator's opinion, the participant is experiencing a clinically significant deterioration in his or her clinical state.
- experiences a Serious Adverse Event deemed to be related to the IMP.
- experiences a severe adverse event deemed to be related to the IMP.
- has an increase in post-enrollment QTcF interval as defined below (see also Section 9.5.8).

Investigational Medicinal Product must be discontinued at any time during the study in the event any of the following are observed post-enrollment:

QTcF Criteria

- A post-enrollment QTcF duration of ≥ 500 ms confirmed by repeat continuous ECG.
- A clinically significant increase of ≥ 60 ms (confirmed by repeat continuous ECG) compared to the average QTcF interval at Baseline (before dosing) is observed.

Participants who have received IMP for longer than 2 weeks and discontinue prematurely any time after Visit 5 should return to the investigational site for final safety and efficacy assessments as scheduled for the EOT visit (Week 13, Visit 16) and complete the study exit form.

Participants who discontinue from the trial prior to receiving any treatment or who discontinue after having received treatment only up to Visit 5 (Week 2 post-baseline) may be replaced.

Participants with early treatment cessation due to SAEs must be followed-up and provided appropriate medical care until their signs and symptoms have remitted or stabilized, or for the remaining study period (until study end), whichever comes sooner. "Study end" is when all participants have completed the study.

9.4.6 Concomitant Therapy

Investigators are encouraged to follow current international and hospital guidelines and current best medical practice for the management of participants with PTHS. Medications should be used per current recommendations. Concomitant medications permitted in the study are outlined below and are described in the Exclusion Criteria (Section 8.2).

Medications prohibited from the study are outlined below and in the Exclusion Criteria (Section 8.2). Participants should not have their existing medication withdrawn in order to enter the study.

Excluded medications/treatments include:

- Current treatment or treatment within the two weeks prior to Screening with MAO inhibitors, d-cycloserine, oxytocin, carbetocin, tricyclic antidepressants, or bupropion.
- Current treatment with more than 3 allowable psychotropic medications.
 - Includes medications used to treat problems with sleep onset and sleep continuity except melatonin. Melatonin for difficulties with sleep onset is permissible and is not included in the count of psychotropic medications.
 - The use of anti-epileptics for other indications such as the treatment of mood disorders counts towards the limit of permitted psychotropic medications.
 - Anti-epileptic medications used for treatment of seizures does not count towards the limit of psychotropic medications.
- Current treatment with insulin or treatment within the last 12 weeks prior to commencement of IMP.
- Current treatment with IGF-1 or treatment within 6 months of commencement of the IMP.
- Current treatment with growth hormone or treatment within 12 months of commencement of the IMP.

The following medications are allowed but must be at stable doses before the start of the study as follows:

- Non-pharmacologic somatic treatment (e.g., a ketogenic diet or vagal nerve stimulation): dosing regimen must be stable at least 4 weeks prior to Screening. If the treatment was discontinued, the discontinuation must have occurred no fewer than 2 weeks before Screening.
- A new behavioral, educational, or cognitive therapy cannot be started during the period of the study or within 4 weeks prior to Screening. Changes to an ongoing treatment regimen that are due to school schedules or are otherwise seasonally related are not exclusionary as long as they are consistent with the typical type and pattern of behavioral treatment received by the participant.
- Seizure medication: dosing regimen must be stable 8 weeks prior to commencing the IMP. Adjustments for changes in weight or age are allowable. If the treatment was discontinued, the discontinuation must have occurred no fewer than 2 weeks before Screening.
- Psychotropics or any other medication used for a chronic illness (not including antibiotics, pain relievers, anti-diarrheals, and laxatives): dosing regimen must have been stable for at least 4 weeks prior to Screening. If the treatment was discontinued, the discontinuation must have occurred no fewer than 2 weeks before the commencement of IMP.
 - o This includes nutraceutical treatments and cannabinoids (THC and CBD) which are allowable but also must meet the stability conditions above.
 - The Investigator should consult with the medical monitor if a participant is being treated with ocular toxic, hepatotoxic medications, nephrotoxic, or antibiotic medications.

The following medications/treatments are permitted and may be adjusted as needed:

- Procedural pain control medication.
- Laxatives and anti-diarrheals.

Standard of care immunizations and vaccinations (including COVID-19) are allowed and are not subject to the above stability conditions.

If the Investigator is unsure if a medication is permitted, the Medical Monitor should confirm if the medication is allowed and will provide written documentation to support the medication's use, if allowed. Concomitant medications will be monitored in a caregiver diary for the approximately 4 to 6 week Screening period to confirm there are no changes from the time of initial screening.

Every effort should be made to maintain stable regimens of concomitant medications and allowed non-medicine-based therapies throughout the course of the study, with the understanding that there will be some changes to non-medicinal treatment regimens that are due to school schedules or are otherwise seasonally related.

Details of concomitant medications will be recorded in the participant notes and in the eCRF.

9.5 Assessments

9.5.1 Vital Signs

Vital signs including weight, blood pressure (SBP and DBP in mmHg), heart rate (bpm), respiratory rate (rpm), and body temperature (°C) will be assessed at the Screening visits (Visits 1 and 2) and at the Baseline visit (Visit 3). Height will be measured at Screening (Visit 1), Baseline (Visit 3) and End of Treatment (Week 13, Visit 16). Blood pressure (SBP and DBP in mmHg), weight, heart rate (bpm), respiratory rate (rpm), and body temperature (°C) will also be assessed at all post-enrollment study visits. If the first dose is administered in clinic the day after the Baseline visit, blood pressure (SBP and DBP in

mmHg), weight, heart rate (bpm), respiratory rate (rpm), and body temperature (°C) should be collected before dosing.

Vital signs will be taken ideally after the participant has been seated for 5 minutes. If this is not feasible, this should be documented in the source notes and the EDC.

The procedures for taking blood pressure will follow best practice from the 2017 American Academy of Pediatrics Clinical Practice Guideline for Screening and Management of High Blood Pressure in Children and Adolescents †††. The clinician conducting the assessments should be trained in the best practice guidelines including how to select the appropriate cuff size. Manual blood pressure measurements from the right arm will be taken by the Investigator or other appropriately credentialed and experienced individual. Ideally, blood pressure should be taken while the participant is seated. The Investigator should ensure to the best extent possible that the participant's feet are flat on the floor, the back is supported, and the right arm supported at level of the heart.

If the manual blood pressure measurements suggest increased blood pressure, an additional blood pressure measurement should be performed manually later in the same visit. If there is a change in blood pressure from baseline, a repeat measurement should be performed manually later in the same visit. The clinician should also document any factors that may affect the blood pressure measurements such as the participant's state (e.g. excited, agitated), disruptive breathing events, hydration level, if the measurements could not be taken seated, or if the participant was uncooperative. If blood pressure measurements suggest elevation, the Investigator should also conduct a medical review with physical exam, and review safety labs, in particular, serum creatinine, urinalysis, and urine volume. If after at least 2 measurements have been taken at the visit, there is confirmed clinical suspicion of true elevation of blood pressure, or if the participant is agitated or uncooperative and the blood pressure cannot be confirmed, or there is a change in blood pressure from baseline, blood pressure should be re-assessed again within 12-24 hours. If elevated blood pressure is confirmed and meets the stopping criteria below, dosing should be discontinued, and a referral should be made to the child's primary care pediatrician or a kidney specialist as deemed appropriate by the Investigator and the Medical Monitor.

IMP must be discontinued at any time during the study in the event that any of the following values are observed on blood pressure exams based upon repeated evaluation on at least three visits.

- For children ages 3-12 years: ≥ 95th percentile (based on height) + 12 mmHg OR ≥ 140/90 mmHg
- For adolescents ages 13 years and above: ≥ 140/90 mmHg (in case a 12-year-old turns 13 years old during the study)

These must be reported and discussed with the Medical Monitor.

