7. STUDY DESIGN

7.1 Study Design Overview

This is a Phase 2, open-label study of the safety and tolerability of NNZ-2591 Oral Solution, 50 mg/mL in male and female children and adolescents with Pitt-Hopkins syndrome. Approximately 10 to 20 male and female participants between the ages of 3 and 17 years will be enrolled and receive treatment of NNZ-2591 Oral Solution, 50 mg/mL for a total of 13 weeks. Additional participants may be screened, enrolled, and treated to achieve approximately 20 study completers.

There will be a total of 17 study visits, comprising 5 in-clinic visits, and 12 remote telemedicine/in-home nurse visits. The study will commence with an approximately 4 to 6 week Screening and Baseline period. During this Screening/Baseline period, participants will be assessed for study eligibility and data will be collected to establish the participant's baseline characteristics and symptom severity using a variety of assessments (Section 9.2). Two in-clinic visits and one remote/in-home visit (Visits 1, 2, 3) comprise Screening and Baseline.

Once eligibility is confirmed, participants will receive the starting dose of 4 mg/kg and then be up-titrated to the target dose (see Section 7.2). Participants will receive treatment for a total of 13 weeks. During the treatment period, there are three in-clinic visits: Week 2 (Visit 5), Week 6 (Visit 9) and Week 13 (Visit 16). There is a combined remote, telemedicine visit by the site investigator and an in-home visit by a visiting nurse for safety at Week 1 (Visit 4), Week 4 (Visit 7), Week 8 (Visit 11) and Week 10 (Visit 13). These combination remote/in-home visits will be conducted simultaneously whenever possible, or they will be conducted on the same day with the telemedicine visit occurring first. If it is not feasible to conduct these visits simultaneously or on the same day, the telemedicine portion of the visit and the nurse portion of the visit must be conducted on two consecutive days. In-home visits with a visiting nurse will be done at Weeks 3 (Visit 6), 5 (Visit 8), 7 (Visit 10), 9 (Visit 12), 11 (Visit 14), and 12 (Visit 15).

All participants will also have a remote post-treatment visit with the Investigator via telemedicine and an in-person home visit by a visiting nurse approximately 2 weeks after the end of treatment (Week 15, Visit 17).

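### Section 9.5.1 leaves the confirmation rule for the mandatory blood-pressure stop open: the stop could fall at a recheck about a day later or, if only scheduled visits count, about two weeks later

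*Protocol*

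**What the plan says.** Two consecutive paragraphs of Protocol Section 9.5.1 (Vital Signs) govern the stop.

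- **Paragraph on elevated readings.** After at least two measurements at the visit, if a true elevation is suspected or cannot be ruled out, "blood pressure should be re-assessed again within 12-24 hours". It continues: "If elevated blood pressure is confirmed and meets the stopping criteria below, dosing should be discontinued", with a referral.
- **Next paragraph.** IMP must be discontinued if the listed age-specific values are observed, "based upon repeated evaluation on at least three visits".

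The same section says that blood pressure "will also be assessed at all post-enrollment study visits". The visible part of Section 9.4.5 (Early Discontinuation) lists QTcF criteria but no blood-pressure criterion, so it does not settle how the two paragraphs fit together.

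**The concern.** The paragraph on elevated readings describes what looks like a decision point: repeat at the visit, recheck within a day, stop if confirmed. The next paragraph ties the mandatory stop to evaluations on three or more visits. Four things are left open: whether the recheck is one of those visits, whether the visits must be scheduled ones, how close together they may be, and whether dosing continues in the meantime. Two sites with identical readings, both acting in good faith, could therefore stop the same child on different days.

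Safety and tolerability, including discontinuations, are primary endpoints (Protocol Section 6.3.1.1). With 10 to 20 participants, one discontinuation is 1/20 = 5% to 1/10 = 10% of the sample. SAP Section 7.6 puts the initial blood-pressure reading in the summary table. All readings go into listings, but nothing in the planned output records which confirmation rule was applied.

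**Working it through.** The plan states no figure for this delay, so there is none to reproduce. The check is calendar arithmetic on the visit schedule.

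**Inputs**
- Visits 4 to 16 fall weekly, at Weeks 1 to 13; Visit 17 is at Week 15, after treatment (Protocol Section 7.1).
- Windows in days: Visits 5 and 9, ±2; Visit 16, −3; Visit 17, +4; the other treatment visits, ±1 (Protocol Table 1).
- Dosing is twice daily and ends by Day 91 (Protocol Section 9.4.2).
- Unscheduled nurse visits may be requested for follow-up (Protocol Section 9.1).

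**Reading A: stop at the recheck.** The decision comes 12 to 24 hours after the first reading, about 1 to 2 doses later.

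**Reading B: three scheduled visits.** Nominal delay = 7 × (week of third visit − week of first). Minimum = nominal − late window of the first − early window of the third. Maximum = nominal + early window of the first + late window of the third.

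| First elevated reading | Third scheduled visit | Nominal (days) | With windows (days) |
|---|---|---|---|
| Visit 4 (Week 1) | Visit 6 (Week 3) | 7 × 2 = 14 | 14−1−1 = 12 to 14+1+1 = 16 |
| Visit 5 (Week 2) | Visit 7 (Week 4) | 7 × 2 = 14 | 14−2−1 = 11 to 14+2+1 = 17 |
| Visit 14 (Week 11) | Visit 16 (Week 13) | 7 × 2 = 14 | 14−1−3 = 10 to 14+1+0 = 15 |
| Visit 15 (Week 12) | Visit 17 (Week 15) | 7 × 3 = 21 | 21−1−0 = 20 to 21+1+4 = 26 |

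Starts at Visits 7 and 9 also give 11 to 17 days. Starts at Visits 6, 8 and 10 to 13 give 12 to 16. For a first elevation at any of Visits 4 to 14, the delay is therefore 14 days nominal and 10 to 17 with windows. At two doses a day, 14 days is 28 doses.

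**Reading C: the recheck counts as one of the three visits.** The third evaluation is the next scheduled visit, 7 days later (14 doses). An unscheduled visit would shorten this further.

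**End of treatment, scheduled visits only.**
- *Visit 15:* the third visit is Visit 17, after dosing has ended, so the three-visit condition cannot act.
- *Visit 14:* the third visit is the end-of-treatment visit, on Day 91 − 3 = 88 at the earliest, so at most about 3 days of dosing remain.
- *Visit 16:* only those same few days remain under any reading, so it hardly separates them.

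**The case against.** The strongest reply is that there is only one rule. The recheck paragraph has no free-standing stop: it requires the elevation to be confirmed and also to meet the criteria that follow, and those criteria include the three visits. On that reading the sequence is a same-visit repeat, a recheck, then a stop once the three-visit condition is met. This is a fair reading, and it means that a flat contradiction, which a reader might infer, is not established. The ambiguity remains even so. The nested rule still does not say whether the recheck or an unscheduled visit counts, or set a time limit, and a site could equally take the recheck as the point of decision.

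The second reply is that two weeks is not what the text requires. It never says that the visits must be scheduled, no scheduled visits lie 12 to 24 hours apart, and unscheduled nurse visits are allowed. That stands: two weeks is the figure for one assumption only.

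The third is that other safeguards exist. Section 9.4.5 lets the investigator stop IMP for an adverse event or tolerability issue and lists clinically significant deterioration. Section 10.5 treats clinically significant vital-sign changes as adverse events. The DSMC reviews safety data before each escalation and after two weeks at the target dose. That also stands. It rules out the inference that a child with elevated pressure could not be stopped sooner, or at all.

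Last, the synopsis says Section 9.4.5 holds renal, ocular and hepatic criteria, and Section 9.5.2 points to a clinical management plan in subsections that are not visible. Removed text may bear on this point; its absence is not an error in the plan.

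**Conclusion.** The point holds as a moderate inconsistency in a mandatory safety rule. Followed as written, Section 9.5.1 can place the stop about 1 day after the first reading (decision at the recheck), about 7 days after (recheck counted as a visit) or about 14 days after, 10 to 17 with windows (scheduled visits only). Unscheduled visits would shorten the last two. On scheduled visits alone, a first elevation at Visit 15 could not meet the three-visit condition before dosing ends.

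These figures describe the blood-pressure rule by itself, assume that elevated readings recur at consecutive visits, and leave investigator judgment aside. A reader might infer that children in this trial were dosed for two extra weeks. The documents do not support that: SAP Section 2.2 says no participant was enrolled under protocol version 3.0, and the blood-pressure wording of the versions they enrolled under is not visible. Safety is summarised descriptively and no planned test depends on this rule. It should be corrected, but it does not undermine the analysis.

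**What to change.** Reconcile the two paragraphs of Section 9.5.1 into one confirmation rule that states:

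- the number of evaluations required;
- whether the 12 to 24 hour recheck and unscheduled visits count as visits;
- the time within which the evaluations must be completed;
- what happens to dosing in the meantime.

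Which rule stands is for the clinical team and the DSMC to decide; this review takes no position on it. In the clinical study report, state which rule governed any discontinuation for blood pressure, including under the protocol versions in force when participants enrolled.

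The cost is one paragraph of protocol wording, a notice to any site still working under it, and a sentence or listing footnote in the report. Because enrollment took place under earlier versions, the reporting step may be the part with most practical effect for this trial.
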